#### d. Primary & Secondary Outcomes

**Primary Outcome.** The primary outcome will be death or neurodevelopmental impairment at 22-26 months. Neurodevelopmental impairment will be defined as any of the following deficits: a cognitive, language or motor score less than 1 SD below the mean on the Bayley Scales of Infant Development III (BSID), gross motor functional (GMF) level ≥1, visual impairment or blindness in any eye, hearing impairment, or seizure disorder. The disability can be mild, moderate, or severe and will be defined as per the NRN standard definitions at the time of assessment (general definitions are listed in Table 7). Assessment will be performed by certified NRN examiners who will be blinded to treatment assignment group. From previous NRN trials, we anticipate a follow-up rate of 90%. At the time of follow-up, a medical history will be obtained; growth parameters and a BSID-III neurological and vision examination will be performed.

**Table 7. Disability definitions**

Disability Severity	Exam Component	Criteria
Mild-to-moderate	Bayley Scales (a)	BSID cognitive score >1 SD below mean but not >2 SD BSID language score >1 SD below mean but not >2 SD BSID motor score >1 SD below mean but not >2 SD
	NF05 Impairment (b)	GMF level of 1 or 2 Any seizure disorder  Any hearing deficit 
	Other impairment (c)	Visual impairment 
Severe	Bayley Scales (A)	BSID cognitive score >2 SD below mean BSID language score >2 SD below mean BSID motor score >2 SD below mean
	NF05 Impairment (B)	GMF level 3 or greater Blindness  Profound hearing loss 

1. Any active or history of seizure(s) or seizure disorder, as noted in history or by chart review.
2. Hearing deficit where there is some amplification required (hearing aids or cochlear implants) in one or both ears as noted by history or chart review that does not reach level of profound hearing loss as defined in the severe category.

3. Visual impairment in one or both eyes per NRN standard follow-up (wears or was prescribed corrective lenses or other abnormality or blind but some functional vision) from chart review or history that does not reach level of blindness as defined in the severe category.
4. Blindness (no useful vision) per NRN standard follow-up as noted by history or chart review.
5. Profound hearing loss per NRN standard follow-up (in any ear as noted by inability to understand commands or communicate with examiner with or without amplification) by history or chart review.

Level of Disability	Definition
Normal	None of either (a) or (b) or (c)
Mild	Any of (a) but none of (b) or (c), OR Any of (b) or (c) but none of (a)
Moderate	At least one from each of (a) and [(b) or (c)]
Severe	At least one of (A) or (B)

**Secondary Outcomes.** Secondary outcomes will include measures of severity of illness using the oxygenation index and respiratory severity score (mean airway pressure X Fio2),  cardiovascular stability (Table 8) and short-term outcomes prior to discharge (Table 9). Measures of short term outcomes and cardiovascular stability will be compared between groups and in relation to each other.

**Table 8. Cardiovascular measures**

Blood Pressure	Blood pressure from before to after study drug administration (continuous)
Heart Rate	Heartrate from before to after study drug administration (continuous)
Fluid (volume) Administration	Presence and number of fluid boluses given prior to study drug and during the study drug administration.
Inotrope Administration	The presence of inotrope initiation & presence of inotrope exposure at days of life 3, 5 & 7 (dichotomous)
Inotrope Duration	Number of total days (complete 24 hours=1 day) an infant remains on any inotrope (continuous)
Inotrope Total Dose	Peak dose in 24-hour periods for 10 days after initiation of study drug.

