- d. Compare measures of cardiovascular sufficiency between those infants on hydrocortisone vs. placebo as measured by pre- and post-study drug differences in blood pressure, the duration and dose of inotropes received, and the presence of metabolic acidosis and oliguria. We **hypothesize** that infants treated with hydrocortisone vs. placebo will have higher blood pressures, receive a lower total dose of inotropes, and/or receive inotropes for a shorter period of time and have less metabolic acidosis and oliguria.

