### e. Sample Size Estimate

Determining a sample size based on available data is limited by the available studies on long-term outcomes including neurodevelopmental impairments or death in term and late preterm infants who have cardiovascular instability and require cardiovascular support. This sample size is based on the best available data, which is closest to the population proposed to study. Based on previous data, the incidence of death or any neurodevelopmental impairment (permanent hearing loss, blindness, moderate or severe cerebral palsy or Bayley MDI or PDI scores <70) was 32% in a similar population of critically ill newborn infants with respiratory distress and in need of mechanical ventilation, but excluding congenital diaphragmatic hernia defects. Based on 4 additional studies in similar populations of term and late preterm infants with respiratory failure, the average incidence of death or any neurodevelopmental impairment was 30%. If these studies had all included mild impairment the event rate would have been higher.

The trial is powered at 80% to detect a reduction in the primary outcome of death or any neurodevelopmental impairment at 22-26 months from 30% to 20%, for a relative risk reduction of 33%, and a relative risk of 0.67, using a two tailed test with 5% Type I error. Allowing for 10% attrition, the required sample size for this scenario is 646 (Table 10). This sample size will also provide >80% power to detect treatment differences in important secondary outcomes of days in the NICU, intubated and on a ventilator and hours on inotropes without adjusting for multiple comparisons (Table 11)."

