### f. Analytical Plan

All analysis will be conducted by intention-to-treat analysis. To ensure that randomization has achieved the desired balance, all demographics will be compared

using Fisher's exact or chi-square tests for categorical factors and t tests or non-parametric tests for continuous outcomes. Dichotomous outcomes including the primary outcome will be compared between the hydrocortisone-treated group and control groups while adjusting for NRN center differences using robust Poisson regression, so that adjusted relative risk estimates of the treatment effect can be obtained. For continuous outcomes, non-normally distributed data may be log-transformed prior to analysis. Secondary analyses may be performed adjusting for gestational age or other critical baseline covariates that may be imbalanced across the two treatment groups, in addition to center. Short-term continuous outcomes will be compared between those receiving hydrocortisone and those on placebo using linear regression adjusting for NRN center and other critical baseline covariates that may be imbalanced.

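### Blood pressure and heart rate are to be compared before and after study drug, but the pre-drug value is not a prespecified covariate, so precision may be lost

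*Combined protocol and SAP*

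**What the plan says.** Specific Aim d (section 4) compares cardiovascular sufficiency between arms, with blood pressure assessed through "pre- and post-study drug differences in blood pressure". Table 8 (section 7.d) lists the blood pressure outcome as "Blood pressure from before to after study drug administration (continuous") and the heart rate outcome as "Heartrate from before to after study drug administration (continuous"). Neither row mentions a covariate.

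Section 7.f (Analytical Plan) compares short-term continuous outcomes "using linear regression adjusting for NRN center and other critical baseline covariates that may be imbalanced". It also says "Secondary analyses may be performed adjusting for gestational age or other critical baseline covariates that may be imbalanced", in addition to center. Gestational age is the only baseline variable named there. Pre-drug blood pressure and heart rate are not named as covariates anywhere in the document.

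**The concern.** A change score subtracts the whole of the baseline value. Unless the baseline predicts the later value one for one, this subtracts too much and adds noise. It also passes part of any chance baseline difference between arms into the estimate. A model with the pre-drug value as covariate estimates how much to subtract.

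The provision for imbalanced covariates does not secure this. It names no blood pressure or heart rate variable, and it depends on what the data show. The precision gained from a prognostic baseline does not depend on imbalance being seen. A covariate set chosen after looking at balance also leaves the model unfixed in advance.

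At stake is the precision of two hemodynamic comparisons. Blood pressure is one of the measures through which Aim d tests whether hydrocortisone improves cardiovascular function.

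**Working it through.** **1. Number of infants available.** The plan gives no sample size, SD of change or power for blood pressure or heart rate. The only relevant figure is the total of 646, set by the primary outcome (30% vs 20%, 80% power, "using a two tailed test with 5% Type I error", 10% attrition).
- Unpooled formula: (0.21 + 0.16) × (1.960 + 0.842)² / 0.10² = 290.4 per arm. Then 2 × 290.4 / 0.9 = 645.4, which rounds up to 646.
- Pooled formula: 294 per arm, giving 647 (× 1.1) or 654 (/ 0.9).

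The figure reproduces. I use 323 per arm, which assumes every infant contributes both readings; deaths and missing readings would lower it.

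**2. Variance ratio.** Let s be the pre-drug SD, k the ratio of post SD to pre SD, and r the pre/post correlation. Per infant, ignoring center (common to both models):
- Change score: s²(1 + k² − 2rk)
- Adjusted for the pre-drug value: s²k²(1 − r²)
- Difference: s²(1 − rk)², which is never negative

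So in large samples adjustment never does worse, and it ties only when rk = 1. With k = 1 the ratio simplifies to (1 + r)/2.

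Neither r nor k is in the documents. Assumed values:

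| r | Ratio, k = 1 | Variance cut | Ratio, k = 1.3 | Variance cut |
|---|---|---|---|---|
| 0.3 | 0.65 | 35% | 1.69 × 0.91 / 1.91 = 0.805 | about 19% |
| 0.5 | 0.75 | 25% | 1.69 × 0.75 / 1.39 = 0.912 | about 9% |
| 0.7 | 0.85 | 15% | 1.69 × 0.51 / 0.87 = 0.991 | about 1% |

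A simulation with k = 1 and 3,000 replicates gave ratios of 0.63, 0.75 and 0.86. With k below 1 the cut is larger than in the k = 1 column. With k = 1 and r of 0.8 or more, it is 10% or less.

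**3. On the blood pressure scale.** Table 3 gives mean blood pressure at first vasopressor dose as 35.6 (SD 7.7, N = 66) below 37 weeks and 39.1 (SD 10.1, N = 149) at 37 weeks or more. Combining the two, including the difference between their means, gives an SD of about 9.55. The table prints no unit; I take mmHg. The detectable difference at 80% power is 2.80 × √(2/323) × SD. With k = 1:

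| r | Change score | Adjusted | Power for an illustrative 2 mmHg: change score, adjusted |
|---|---|---|---|
| 0.3 | 2.49 | 2.01 | 61%, 80% |
| 0.5 | 2.11 | 1.82 | 76%, 87% |
| 0.7 | 1.63 | 1.50 | 93%, 96% |

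The post-drug value alone would give 2.11 mmHg. So with equal SDs and r below 0.5, an unadjusted change score does worse than ignoring baseline.

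**4. Chance imbalance.** The SE of the baseline difference between arms is 9.55 × √(2/323) = 0.75 mmHg. An unadjusted change score carries −(1 − rk) times that difference. With k = 1 and r = 0.5, an imbalance of 1.5 mmHg (2 SE) moves the estimate by 0.75 mmHg. Randomization is stratified by center only, and Table 3 shows pressure differing with gestational age.

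**5. Choice of outcome.** Regressing change on treatment plus the pre-drug value gives the same treatment estimate as regressing the post-drug value on the same terms. The simulation agreed to rounding error. The outcome definition therefore need not change.

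**The case against.** The strongest reply is that the plan does not clearly commit to an unadjusted change score. Table 8 never uses the word *change* and could be describing a measurement window. Only Aim d speaks of differences, and only for blood pressure, so for heart rate the reading is inferred from parallel wording. Section 7.d also lists the Table 8 measures separately from the short-term outcomes of Table 9, and the linear regression in section 7.f is stated for short-term continuous outcomes. It may not govern Table 8 at all. If it does, its allowance for other baseline covariates could admit the pre-drug value. All of this stands. It makes the plan silent or conditional rather than committed to the weaker analysis, but on no reading is the pre-drug value prespecified.

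The size is also open to challenge. The 15% to 35% range needs equal SDs as well as an assumed correlation, and it shrinks quickly if the post-drug SD is larger. The SDs in step 3 come from an observational cohort at first vasopressor dose, not from trial infants just before study drug. Even with equal SDs, the detectable difference improves by only 0.13 to 0.48 mmHg.

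Three stronger readings are tempting and not supported:
- A reader might infer that regression to the mean biases the result, because infants enter when unstable. In a randomized, masked, placebo-controlled trial it acts on both arms alike. It distorts within-arm change, not the contrast between arms.
- A reader might infer that the trial needs more infants. The total is set by the primary outcome, and neither blood pressure nor heart rate appears among the secondary outcomes sized in Table 11.
- A reader might treat the adjusted blood pressure difference as the answer to Aim d. That aim also covers inotrope dose and duration, metabolic acidosis and oliguria, and it does not mention heart rate.

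**Conclusion.** The point holds as a gap in prespecification that can cost precision in secondary outcomes. The validity of the randomized comparison is not in question. Relative to an unadjusted change score, adjusting for the pre-drug value would cut variance by 35% to 15% for correlations of 0.3 to 0.7 with equal pre and post SDs, and by about 19% to 1% if the post SD is 1.3 times the pre SD. Both the correlation and the SD ratio are assumptions. The direction is firmer than the size: in large samples the adjusted analysis is at least as precise as the change score, and it removes the linear effect of chance imbalance in the pre-drug value. The gain is worth having at low to moderate correlation and minor at high correlation or with a larger post-drug SD.

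**What to change.** Add to section 7.f that the between-arm comparisons of blood pressure and heart rate will use linear regression with the pre-drug value of the same measure and NRN center as prespecified covariates, whether or not imbalance is observed. Naming the two outcomes also settles whether the model covers Table 8. The outcome may stay as change from the pre-drug value. Report the adjusted differences alongside the other Aim d measures, not as the sole result for that aim.

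The cost is one sentence and one degree of freedom per model. No new data are needed, because the pre-drug reading is already required to form the outcome.

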**Table 9. Short-term outcomes**

Duration of mechanical ventilation	Number of days of laryngeal intubation and mechanical ventilation
Days to full feeds	Day of age when enteral feeds ≥ 120 cc/kg/day (continuous)
Need for gastrostomy tube	Need for gastrostomy tube before discharge (dichotomous)
Duration of O2 requirement	Number of days on oxygen while in hospital (continuous)
Need for home oxygen	Infant was discharged to home on oxygen (dichotomous)
Length of hospital stay	Number of days from birth to date of first discharge (continuous)
Renal insufficiency	Presence of creatinine >2.0 in first 7 days of age (dichotomous)
NEC	Presence of NEC stage II or greater at any time prior to discharge (dichotomous)
Death	Presence of death before discharge (dichotomous)
Head imaging	Any result from head imaging performed by the clinical care team (head ultrasound, magnetic resonance imaging, CT scan); no abnormalities noted, IVH, PVL
ECMO therapy	ECMO administered at any time while in hospital

### e. Sample Size Estimate

Determining a sample size based on available data is limited by the available studies on long-term outcomes including neurodevelopmental impairments or death in term and late preterm infants who have cardiovascular instability and require cardiovascular support. This sample size is based on the best available data, which is closest to the population proposed to study. Based on previous data, the incidence of death or any neurodevelopmental impairment (permanent hearing loss, blindness, moderate or severe cerebral palsy or Bayley MDI or PDI scores <70) was 32% in a similar population of critically ill newborn infants with respiratory distress and in need of mechanical ventilation, but excluding congenital diaphragmatic hernia defects. Based on 4 additional studies in similar populations of term and late preterm infants with respiratory failure, the average incidence of death or any neurodevelopmental impairment was 30%. If these studies had all included mild impairment the event rate would have been higher.

The trial is powered at 80% to detect a reduction in the primary outcome of death or any neurodevelopmental impairment at 22-26 months from 30% to 20%, for a relative risk reduction of 33%, and a relative risk of 0.67, using a two tailed test with 5% Type I error. Allowing for 10% attrition, the required sample size for this scenario is 646 (Table 10). This sample size will also provide >80% power to detect treatment differences in important secondary outcomes of days in the NICU, intubated and on a ventilator and hours on inotropes without adjusting for multiple comparisons (Table 11)."

**Table 10. Enrollment/time/consent estimates**

Reduction in death or neurodevelopment delay at 22-26 mo	Total enrollment (including 10% loss)	Months to complete enrollment if consent rate 60%	Months to complete enrollment if consent rate 70%
10%	646	48	41

Because of the lack of data on outcomes in this population with which to ascertain power calculations with high confidence, the overall event rate of any NDI or death in this population will be calculated either: 1 year after the first patient is evaluated at 22-26 month follow-up or after 30% of a planned enrollment of 646; whichever occurs first. At this point, the number needed to achieve 80% power, to detect a difference of 10% with an alpha of 0.05 and a 2 sided t-tail test, will be recalculated.

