**Table 6-1. Outcomes in infants who received inotropes vs. those who did not**

Outcome	All Infants N=783	Inotropes N=212	No inotropes N=571	P-value
Death, %	6.8 (53/778)	15.7 (33/210)	3.5 (20/568)	<.0001
Died within 7 days, %	3.0 (23/778)	8.6 (18/210)	0.9 (5/568)	<.0001
Age at time of death	9.0 (3.0, 26.0)	7.0 (3.0, 11.0)	25.5 (8.0, 52.5)	0.0054
Days intubated and on vent	3.0 (2.0, 8.0)	8.0 (4.0, 13.0)	2.0 (2.0, 5.0)	<.0001
Days on oxygen	6.0 (2.0, 11.0)	10.0 (6.0, 17.0)	4.0 (2.0, 8.0)	<.0001
Day of life at time of full nipple feeding	9.0 (6.0, 17.0)	16.0 (10.0, 26.0)	8.0 (5.0, 14.0)	<.0001
Days in NICU	12.0 (8.0, 24.0)	16.0 (10.0, 34.0)	11.0 (8.0, 21.0)	<.0001

**Table 6-2. Outcomes in infants by gestational age who received inotropes vs. those who did not; excluding infants with CDH, HIE, receipt of whole body cooling, and omphalocele,**

Outcome	All Infants	Inotropes	No Hypotension by any definition	* signified p-value is <0.5 between groups
GA < 37 weeks	N = 277	N = 42	N = 115	
Death (%)	3.2	14.3	0 (0/115)	*
Died within 7 days (%)	1.4	9.5	0 (0/115)	*
Age at time of death 	9 (4, 16)	4 (3, 16)	NA	NA
Days intubated and on ventilator	2 (2, 5)	7 (4, 11)	2 (2, 4)	*
Days on oxygen	5 (2, 9)	10.5 (4, 16)	4 (2, 8)	*
DOL at time of full nipple feeding	9 (6, 17)	20.5 (10, 27)	8 (6, 14)	*
Days in NICU	12 (8, 24.5)	16 (10, 34)	10 (6, 17)	*

GA ≥ 37 weeks	N = 370	N = 93	N = 113	
Death (%)	4.3	9.8	2.7	*
Died within 7 days (%)	1.4	4.4	0.0	*
Age at time of death	12.5 (2, 45.5)	12 (2, 18)	48 (30, 60)	
Days intubated and on ventilator	3 (2, 8)	9.5 (4, 13)	2 (1, 4)	*
Days on oxygen	5 (2, 10)	11 (8, 18.5)	3 (1, 5)	*
DoL at time of full nipple feeding	8 (5, 15)	14 (10, 26)	6 (3, 9)	*
Days in NICU	12 (7, 21)	17 (11, 35)	8 (5, 15)	*

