#### **h. Estimated Recruitment Time**

With 60% consent, 48 months would be needed to enrollment goal. Anticipating delays in startup and missed infants, study enrollment should be completed in a little over four years.

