Serious adverse events to be reported to NICHD within 24 hours include death, late onset sepsis, hyperglycemia receiving insulin, hypertension receiving antihypertensive medication or intestinal perforation with an assessment as best as possible as to the cause of the perforation (NEC, spontaneous, other).

b. Interim safety monitoring

The DSMC will compare the incidence of death and a composite of serious adverse events including death, late onset sepsis, intestinal perforation, and hyperglycemia requiring insulin between the two treatment arms after every 100th infant reaches status (death, discharge, transfer or 60 days of age). Since 646 infants are to be enrolled in this trial, this will involve interim looks approximately once every 9 months, or after the enrollment of every additional 160 infants, giving a Pocock boundary of 2.413, with a corresponding significance level of  $p<0.0158$  (Pocock, 1977). Such reports will be forwarded to the Chair of the DSMC when there is any suggestion of a trend towards a difference between the two treatment arms emerging. They will also be made available to the full DSMC at their scheduled meetings after 50% and 75% of the trial infants reach status as defined by the GDB. Interim efficacy analysis using O'Brien-Fleming stopping bounds will also be made available to DSMC when 50% of primary outcome data is available.

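### As written, the sample-size recalculation is triggered at 30% of enrolment (about month 12–14), before any survivor can have the 22–26 month assessment that it depends on

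*Combined protocol and SAP*

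**What the plan says.** Section 7e admits that outcome data in this population are too thin to fix the event rate with confidence. As a safeguard, "the overall event rate of any NDI or death in this population will be calculated either" of two time points: "1 year after the first patient is evaluated at 22-26 month follow-up or after 30% of a planned enrollment of 646; whichever occurs first". Then: "At this point, the number needed to achieve 80% power, to detect a difference of 10% with an alpha of 0.05", two-sided, is worked out again.

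The surrounding facts are these:

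- Section 7d sets the primary outcome at 22–26 months and expects 90% follow-up.
- Section 7b caps age at randomisation at 96 hours, so time since randomisation is close to age.
- Table 10 gives 48 months to full enrolment at 60% consent and 41 months at 70%. Section 7h repeats the first figure ("With 60% consent, 48 months would be needed to enrollment goal") and allows for a total a little over four years.
- No section says that the 30% refers to infants who have completed follow-up, and none defines a substitute for impairment status before the 22–26 month visit.

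**The concern.** The rule takes the earlier of two limbs. One is tied to follow-up visits and the other to enrolment. With a two-year outcome and a four-year accrual, the enrolment limb is reached long before anyone has been followed up. The recalculation would then be due when the rate it needs does not exist.

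This matters because the step is the plan's stated check on an event rate that it calls uncertain. Section 7e takes 30% from earlier studies, the main one of which counted Bayley scores below 70 and moderate or severe cerebral palsy. The trial counts any score more than 1 SD below the mean and gross motor level 1 or above. Section 7e itself notes: "If these studies had all included mild impairment the event rate would have been higher". Under a fixed 10-point difference, a higher rate calls for more infants.

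If the trigger fires with only deaths known, the trial team must skip the step, postpone it, or use some other rate. The plan does not say which.

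**Working it through.** **The plan's own sample size.** Inputs (section 7e): 30% versus 20%, 80% power, two-sided 5%, 10% attrition; 1:1 allocation (section 7a). With unpooled variance, n per arm = (1.960 + 0.842)² × (0.30×0.70 + 0.20×0.80) / 0.10² = 7.849 × 0.37 / 0.01 = 290.4. Dividing by 0.9 gives 322.7, rounded up to 323 per arm, or 646. The planned figure reproduces. The problem is the trigger, not the original calculation.

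**When each limb falls.** 30% of 646 = 193.8, i.e. 194 infants. Month reached = 193.8 ÷ monthly accrual.

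| | 60% consent | 70% consent |
|---|---|---|
| Accrual per month | 646/48 = 13.46 | 646/41 = 15.76 |
| 30% enrolled | month 14.4 | month 12.3 |
| Earliest survivor assessment | month 22 | month 22 |
| Gap | 7.6 months | 9.7 months |
| One year after first evaluation | months 34–38 | months 34–38 |

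The last row is 22 + 12 to 26 + 12.

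**Does the order depend on pace?**

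- Section 7g expects 22–25 eligible infants per month. At 60–70% consent that is 13.2–17.5 enrolled per month, which puts 30% at about months 11–15.
- If accrual took 60 months (assumption), 30% would fall at month 18.0.
- For 30% to wait until month 22, steady accrual would have to be 193.8/22 = 8.8 per month or fewer, about 73 months in total.
- For the follow-up limb to come first, accrual would have to be 193.8/34 = 5.7 per month or fewer, about 113 months in total.
- If accrual rose linearly to 13.46 per month over the first 18 months (assumption), 121 would be enrolled by month 18. The other 72.7 take 5.4 months, so 30% falls at month 23.4. Infants then past 22 months: 0.5 × (13.46/18) × 1.4² = 0.7, about one infant.

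**What the 10-point rule returns at other pooled rates.** Same formula, with arms 5 points either side of the pooled rate, n per arm rounded up, doubled and divided by 0.9:

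| Pooled rate | N |
|---|---|
| 9.8% | 300 |
| 11.2% | 340 |
| 14.3% | 420 |
| 25% (design) | 647 |
| 30% | 724 |
| 35% | 787 |
| 40% | 829 |

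The 647 differs from 646 only in the order of rounding. The first three rates are illustrative. They are the death rates in the inotrope groups of Table 6-2 ("excluding infants with CDH, HIE, receipt of whole body cooling, and omphalocele"): 9.8% at term, 14.3% before 37 weeks, and the weighted mean (42×14.3 + 93×9.8)/135 = 11.2%. The rates of 30–40% are assumptions.

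**The case against.** The best answer is that the authors meant 30% of 646 with a known outcome. A rate of death or impairment presupposes outcomes, and the numbers lend support. One year after the first evaluation, about 12 months of accrual (162–189 infants, 25–29% of 646) are due for assessment, so the two limbs would nearly coincide. On the literal reading the follow-up limb could never apply at the planned pace. Section 8b also uses enrolment loosely: it sets safety looks by infants reaching status and then describes them by infants enrolled.

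That reading is plausible, but the text does not carry it. The rule names planned enrolment. Where section 8b means known outcomes for the efficacy look, it says so: the analysis "will also be made available to DSMC when 50% of primary outcome data is available". If the benign reading is right, the same one-sentence clarification settles it.

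Two further objections stand in part. Nothing suggests that the team would substitute a death rate for the composite, so the N of 300–420 shows only the direction of that error and is not a forecast. And a slow enough start could move the trigger just past month 22. However, the 18-month ramp above adds about 9 months to accrual, more than section 7h allows for, and still leaves about one infant assessable.

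**Conclusion.** The point holds. At every steady pace that the documents support, the enrolment limb fires first: month 12.3–14.4 on Table 10's figures, about 8–10 months before any survivor can be assessed and about 20–26 months before the follow-up limb (34 − 14.4 = 19.6 to 38 − 12.3 = 25.7). The rate that the step requires cannot then be computed, and the plan gives no fallback.

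The conclusion rests on the wording as it stands, roughly uniform accrual, and a first assessment no earlier than 22 months. It is confined to the sample-size safeguard and does not touch the primary analysis or the safety monitoring. It should be fixed, because this is the plan's stated check on an event rate that the authors expect may be too low.

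**What to change.** Reword the second limb of section 7e so that it is reached when 30% of 646 (194 infants) have a known primary outcome, meaning death or a completed assessment, counting only infants whose 22–26 month window has closed. State that the rate is pooled, masked, and computed among window-closed infants only. Otherwise early deaths, which are known at once, would be over-represented.

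The change is one sentence. Its costs are timing and precision:

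- **The follow-up limb then governs**, at about months 34–38. The reworded limb falls later, at (193.8/0.9)/13.46 + 26 = month 42.0 (60% consent) or (193.8/0.9)/15.76 + 26 = month 39.7 (70% consent). This assumes 90% follow-up and windows closing at 26 months. By then 42/48 = 88% or 39.7/41 = 97% would be enrolled. Deleting the second limb would therefore have the same effect at the planned pace and is a simpler alternative.
- **Enrolment is well advanced at months 34–38:** 71–79% (60% consent) or 83–93% (70% consent).
- **Few outcomes are in.** Windows closed: 108–162 infants (60% consent) or 126–189 (70% consent). At 60% consent and 90% follow-up that is about 97–145 known outcomes. A pooled rate of 25% then has a 95% half-width of 1.96 × √(0.25×0.75/n), or 8.6 points at n = 97 and 7.0 points at n = 145.

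So late a check can mainly support an increase in sample size or a restated power, not a reduction. The section should say so.
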